#### 9.4.2 Safety analyses

All safety analyses will be performed on the safety analysis set. Key safety analyses will be repeated using the SAF-LTE analysis set.

The primary objective of the study to evaluate the long-term safety and tolerability of tezepelumab in severe asthma subjects will be assessed through on-treatment AEs (including AESIs, as defined in Section 8.3.8) and SAEs. AEs, AESIs and SAEs will be summarized using exposure adjusted incidence rates (i.e., number of subjects reporting events divided by person-time at risk) to account for the variability in follow-up. CCI

The definition of on-treatment AEs and post-treatment AEs will be defined in the SAP.

The treatment groups for addressing the primary objective will be “Randomized Tezepelumab” and “Randomized Placebo” using the safety analysis set. Supportive analysis of key safety data will be presented for the “Tezepelumab Predecessor+Tezepelumab LTE” and “Placebo Predecessor+Placebo LTE” treatment groups using the SAF-LTE analysis set. Summaries for these 4 treatment groups will be provided overall (Week 0 to Week 104) and by time period

Tezepelumab - D5180C00018

(Week 0 to Week 52/48, Week 52/48 to Week 104). An additional summary of key safety data will be provided for the “Placebo Predecessor+Tezepelumab LTE” treatment group for the SAF-LTE analysis set by time period (Week 0 to Week 52/48, Week 52/48 to Week 104) only.

CCI The “All Tezepelumab” treatment group may additionally be used to report AESIs (rare events) for the safety analysis set. In addition, AESIs may be assessed using the pooled data across the 2 studies.

Laboratory data will be summarized by presenting shift tables using normal ranges (baseline in predecessor study to most extreme post-baseline value) and by presenting summary statistics of observed and change from baseline values (means, medians, quartiles, ranges). The incidence of clinically notable laboratory abnormalities will be summarized.

Further details on additional analyses and presentation of safety data will be provided in the SAP.

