The treatment groups for addressing the secondary objective will be “Randomized Tezepelumab” and “Randomized Placebo” using the full analysis set. A supportive analysis will be performed using the “Tezepelumab Predecessor+Tezepelumab LTE” and “Placebo Predecessor+Placebo LTE” treatment groups based on the FAS-LTE analysis set. Asthma exacerbation rates overall (Week 0 to Week 104) and by time period (Week 0 to Week 52/48, Week 52/48 to Week 104) will be presented for the “Randomized Tezepelumab” and “Randomised Placebo” treatment groups, as well as the “Tezepelumab Predecessor+Tezepelumab LTE” and “Placebo Predecessor+Placebo LTE” treatment groups. Any further supportive analyses of the secondary objective, such as assessing different treatment groups, will be specified in the SAP.

CCI

9.4.4

CCI

CCI

Tezepelumab - D5180C00018

**9.4.4.1** CCI [REDACTED]

CCI [REDACTED]

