1 STUDY DETAILS

[figure not shown]
This statistical analysis plan (SAP) for study D5180C00018 outlines the statistical analyses specified in the latest version of the Clinical Study Protocol (CSP) in more detail; any changes to what is specified in the CSP will be described in Section 6.

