1.2 Study design

This is a multicentre, randomised, double-blind, placebo controlled, parallel group, phase 3 LTE study designed to evaluate the safety and tolerability of 210 mg Q4W (SC) of tezepelumab in adults and adolescents with severe, uncontrolled asthma on medium to high-dose ICS and at least one additional asthma controller with or without OCS. Subjects who have continued to receive investigational product and have attended the End of Treatment (EOT) visit in one of the predecessor studies, week 52 in study D5180C00007 or week 48 in study D5180C00009, on investigational product (IP) may be eligible to enrol into this study if they fulfil the inclusion/exclusion criteria.

[figure not shown]
The aim of this study is to evaluate the safety and efficacy over 104 weeks. Data from the predecessor studies will be integrated with the data from DESTINATION but will be reported separately for subjects enrolled in D5180C00007 from those enrolled in D5180C0009 unless otherwise stated explicitly.

This study will be run at approximately 350 sites worldwide and will randomise approximately 975 subjects worldwide. All subjects will be re-randomised in this study to maintain the blinding. Subjects previously randomised to the 210 mg tezepelumab Q4W SC arm in either of the predecessor studies, will be assigned to remain on 210 mg tezepelumab Q4W SC dosing in DESTINATION. Subjects randomised to placebo arm in the predecessor studies will be re-randomised in a 1:1 ratio to either 210 mg tezepelumab or placebo, both administered Q4W SC. Given the randomisation scheme of subjects in the predecessor studies, this will give an overall subject distribution of 3:1 (tezepelumab:placebo), assuming a similar number of subjects rollover from each arm in the predecessor studies. See Figure 1 below for the general study design.

Figure 1 Study Design

| Week 0-48 Week 52 V | LONG TERM EXTENDED (LTE) STUDY | | | | | | |
|----------------------------|--------------------------------|------------------------------------|---------------------|-----------|----------|-----|--|
| | Predecessor EOT/V1 | V2 | V3 - V14 | V15 | V16, V17 | CCI | |
| | Week 52 Visit (D5180C00007) | | Week | Week | Week | | |
| Week 0-44 (D5180C00009) | | Week 52 for D5180C00009 only | W | 104 | 110, 116 | | |
| Treatment Phase | Treatment Phase | | End of Treatment | Follow-up | | | |

V: Visits

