2.1.2 Treatment groups

There are 5 possible groupings across the predecessor and LTE studies as shown in Figure 2 below.

Figure 2 Treatment groupings

[figure not shown]

Note: Groups 2 and 5 reflect subjects in the predecessor studies who do not enrol in the LTE study.

The following treatment groups for analyses will be considered, where time from first dose is applicable for the safety analysis, and time from randomisation is applicable for the efficacy analysis:

Primary (based on the SAF and FAS analysis sets):

[figure not shown]
- Randomised Tezepelumab (Rand Teze): All subjects originally randomised to tezepelumab in the predecessor studies. Will include all data from first dose/randomisation in the predecessor studies to end of the LTE study. (A, B and C)
- Randomised Placebo (Rand Pbo): All subjects originally randomised to placebo in the predecessor studies. Will include all data from first dose/randomisation in predecessor studies up until switch to tezepelumab, and all data from first dose/randomisation in the predecessor studies to end of the LTE study for subjects randomised to placebo in the predecessor studies and the LTE study. (D, F, G and H)

Supportive (based on the SAF-LTE and FAS-LTE analysis sets):

[figure not shown]
- Tezepelumab Predecessor+Tezepelumab LTE (Teze+Teze): All subjects originally randomised to tezepelumab in the predecessor studies and re-randomised to tezepelumab in the LTE study. Will include all data from first dose/randomisation in the predecessor study to end of the LTE study for only subjects enrolled into the LTE study. (A and B)
- Placebo Predecessor+Placebo LTE (Pbo+Pbo): All subjects randomised to placebo in the predecessor studies, and later re-randomised to placebo in the LTE study. Will

include all data from first dose in predecessor studies until end of the LTE study for only subjects enrolled into the LTE study. (F and G)

[figure not shown]
Supportive (for exposure summaries and rare events based on the SAF analysis set):

[figure not shown]
• All Tezepelumab (All Teze): All subjects randomised to tezepelumab in the predecessor studies and subjects randomised to tezepelumab in the LTE study. It will include all data from time of first dose/randomisation to tezepelumab. (A, B, C and E)

Additional (for the assessment of durability of benefit based on the SAF-LTE and FAS-LTE analysis sets):

- Tezepelumab Predecessor+Tezepelumab LTE (Teze+Teze): as defined above

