4.5 Safety and tolerability

4.5.1 Adverse events

AEs will be summarised separately for the on-treatment and on-study periods as defined in Section 3.2.2 unless stated otherwise. All AE summaries will be presented by analysis set and treatment groups as follows:

- SAF (Randomised Tezepelumab and Randomised Placebo), overall only
- SAF-LTE (Tezepelumab Predecessor+Tezepelumab LTE and Placebo Predecessor+Placebo LTE), overall and by time period
- SAF-LTE (Placebo Predecessor+Tezepelumab LTE), predecessor and LTE periods

All AEs will be listed for the SAF-LTE analysis set. AEs occurring during the screening/runin period or occurring post-treatment will be highlighted with an asterisk in the listing, but
not summarised separately. In addition, for subjects with a delay between the predecessor
study EOT visit and LTE study Visit 1, a listing of AEs starting more than 33 days after the
last dose of IP in the predecessor study but prior to Visit 1 in the LTE study will be provided.
A further listing of AEs occurring between the LTE study Visit 1 and the date of first dose in
the LTE study will be provided for those subjects who do not receive their first dose of IP in
the LTE study at Visit 1 of the LTE study. Information related to the outcome of any
pregnancies will also be listed for the SAF-LTE analysis set.

For each of the summaries below, the following will be included:

- Number and percentage of subjects reporting at least one AE.
- Exposure adjusted incidence rates (as defined in Section 3.2.2) per 100 subject-years

An overall summary table will be produced showing the following categories: any AEs, serious adverse events (SAEs), AEs with a fatal outcome, and AEs leading to discontinuation of IP (DAEs).

All AEs will be summarised by system organ class (SOC) and preferred term (PT) assigned to the event using the MedDRA dictionary. For each PT, for the number of subjects reporting at least one occurrence of the event, subjects with multiple occurrences of the same PT will only be counted once for the calculation of incidence rates.

Similar summaries by SOC and PT will also be presented for:

- SAEs
- Fatal AEs
- DAEs on-treatment period only

- DAEs causally related to IP on-treatment period only
- SAEs leading to discontinuation of IP on-treatment period only
- Each AESI category separately on-treatment period only

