6 CHANGES OF ANALYSIS FROM PROTOCOL

• A new analysis set "LTE analysis set" has been added to the SAP to show the full disposition of subjects from the predecessor studies, and to allow for the possibility that subjects may be enrolled or randomised in the LTE study but do not take IP in the LTE study.

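### The SAP drops, undeclared, the by-period AE summaries the protocol requires for the primary safety groups, whose overall rates mix the two study years in different proportions

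*SAP*

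**What the plan says.** **Protocol 9.4.2** names Randomised Tezepelumab and Randomised Placebo, in the safety analysis set (SAF), as the groups for the primary objective. It adds two supportive groups in SAF-LTE (tezepelumab throughout, placebo throughout) and then states: "Summaries for these 4 treatment groups will be provided overall (Week 0 to Week 104) and by time period". The periods are Week 0 to Week 52/48 and Week 52/48 to Week 104.

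**SAP 4.5.1** lists the AE presentations. For the two primary groups the entry is "SAF (Randomised Tezepelumab and Randomised Placebo), overall only". Table 10 in SAP 8.4 agrees: these groups have only an Overall column for AEs. The supportive SAF-LTE groups keep both overall and by-period summaries.

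**SAP Section 1** says that "any changes to what is specified in the CSP will be described in Section 6". Section 6 has one entry, a new LTE analysis set that "has been added to the SAP to show the full disposition of subjects from the predecessor studies". No readable row of the SAP amendment history reports the removal of by-period AE tables for the primary groups.

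**SAP 2.1.2** sets what the placebo group contributes: "Will include all data from first dose/randomisation in predecessor studies up until switch to tezepelumab". Subjects who stay on placebo contribute through the LTE. **SAP 3.2.2** defines the exposure-adjusted incidence rate as subjects with an event over total exposure, with each subject counted once per event type.

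**The concern.** Two things come together here. The first is an undeclared departure from the protocol on the primary objective. It is not a limit of the table format, because the same Table 10 gives these two groups a by-period presentation for laboratory and vital-sign summaries.

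The second is that the two primary groups do not share the same calendar of exposure. Predecessor placebo subjects who enter the LTE are "re-randomised in a 1:1 ratio to either 210 mg tezepelumab or placebo", and those sent to tezepelumab leave the Randomised Placebo group at that point. Randomised Placebo therefore has about half the LTE exposure of Randomised Tezepelumab per subject originally randomised. Any AE whose frequency differs between the first and second year then shows a difference between arms in the overall rate even if the drug does nothing. A period split lets a reader see this. The primary AE table, as the SAP now has it, gives no sign of it.

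**Working it through.** **Inputs**
- Roll-over share f = 0.90 × 0.90 = 0.81 (Protocol 9.2; SAP 1.3).
- 1:1 re-randomisation of predecessor placebo subjects (SAP 1.2).
- Period lengths: 52 + 52 weeks for D5180C00007 and 48 + 56 weeks for D5180C00009 (Protocol 4.1).
- Assumed, since the LTE dropout rates are redacted: equal roll-over by arm, and equal mean LTE exposure per entrant in both arms.

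**Reproducing the plan's own figures.** With equal predecessor arms, LTE allocation is (1 + 0.5) : 0.5 = 3:1, as SAP 1.2 states. Expected enrolment is 860 + 115 = 975, as stated. The documents give no AE rate ratio to reproduce.

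**Person-time shares, D5180C00007, per subject originally randomised**
- Tezepelumab: 1 year predecessor + 0.81 year LTE. LTE share 0.81/1.81 = 0.448.
- Placebo: 1 year predecessor + 0.405 year LTE. LTE share 0.405/1.405 = 0.288.

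**AE confined to the LTE, no drug effect.** Let P and L be the mean predecessor and LTE exposure, and p the probability of the event per LTE entrant.

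Ratio = [f·p/(P + f·L)] / [0.5·f·p/(P + 0.5·f·L)] = (2P + f·L)/(P + f·L), so p cancels.

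| Case | Ratio |
|---|---|
| D5180C00007, f = 0.81: 2.81/1.81 | 1.55 |
| D5180C00007, f = 1: 3/2 | 1.50 |
| D5180C00009, f = 0.81: (96 + 45.36)/(48 + 45.36) | 1.51 |
| D5180C00009, f = 1: (96 + 56)/(48 + 56) | 1.46 |
| D5180C00007, f = 0.81, assumed P = 0.95 and L from 1.0 down to 0.85 | 1.54 to 1.58 |

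The ratio rises towards 2.0 as roll-over falls. The crude percentage of subjects, shown in the same tables, has ratio f·p/(0.5·f·p) = 2.0. An AE confined to the predecessor year goes the other way: 1.405/1.81 = 0.78 for D5180C00007 and (48 + 22.68)/(48 + 45.36) = 0.76 for D5180C00009.

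**AE present in both years, LTE hazard r times the predecessor hazard, rare event.**

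Ratio = [(1 + 0.81r)/1.81] / [(1 + 0.405r)/1.405]
- r = 0.5: 0.91
- r = 2: 1.12
- r = 5: 1.30

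**The same with each subject counted once.** For predecessor hazard h per year, let q1 = 1 − exp(−h) and q2 = 1 − exp(−h − rh).

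Ratio = {[0.19·q1 + 0.81·q2]/1.81} / {[0.595·q1 + 0.405·q2]/1.405}

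| h per year (assumed) | r = 2 | r = 5 |
|---|---|---|
| 0.1 | 1.10 | 1.24 |
| 0.3 | 1.04 | 1.14 |
| 0.6 | 0.98 | 1.02 |

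The upward bias fades as the AE becomes common. For an AE that declines it does not fade: r = 0.5 with h = 0.3 gives 0.88.

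**LTE period alone.** (f·p/f·L) / (0.5·f·p/0.5·f·L) = 1.00. The retained SAF-LTE table already gives this comparison. By the definitions in SAP 2.1.2, the LTE data of Randomised Tezepelumab come only from the tezepelumab-throughout group, and those of Randomised Placebo only from the placebo-throughout group. SAP 3.1.5.1 counts subjects never dosed in the LTE in the predecessor period only.

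**The case against.** The strongest reply is that little information is lost.

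- **The distortion is not the SAP's doing.** It sits in the overall rate, which the protocol itself plans. Restoring the columns leaves that rate unchanged. This stands: the SAP removes a check on the rate but does not create the bias.
- **The LTE comparison survives.** A reader might infer that an LTE-only imbalance could no longer be checked. That is not so, because the LTE column in SAF-LTE rests on the same subjects. This also stands, although nothing in the primary table points there.
- **COVID-19 is covered.** SAP 8.5 splits the AE overview, and AEs and SAEs by SOC and PT, into before and during the pandemic. These tables are for SAF-LTE, so they help, but they leave the primary table without a split.
- **Only a rare AE gives the larger ratios.** This is correct for AEs that rise over time, as the count-once table shows.

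Two wider readings are also tempting. One is that by-period exacerbation rates for the randomised groups (Protocol 9.4.3) were dropped as well. The readable SAP gives them only for FAS-LTE, but the exacerbation rows of Table 10 are redacted, so this cannot be established. The other is that the narrowing of important deviations to SAF-LTE was concealed. The SAP amendment history records it (28-Oct-20); it is only missing from Section 6.

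What the reply does not answer is the SAF predecessor-period column. It includes subjects who never rolled over, whom SAF-LTE leaves out. It cannot be obtained by subtraction, because a subject with events in both periods counts once overall. Protocol 9.3 also warns that the LTE subsets may be selected and keeps them for supportive use.

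**Conclusion.** The point holds as an undeclared departure on the primary safety presentation, made more important by a known period imbalance between the arms. At the planned roll-over, the overall rate ratio under no drug effect is about 1.55 for a rare LTE-only AE in D5180C00007 and 1.51 in D5180C00009. It is about 1.1 to 1.3 for rare AEs whose hazard rises 2- to 5-fold, and nearer 1 for common AEs that rise. AEs that fade are biased the other way, to about 0.9 for a halved hazard when the AE is rare. These figures assume equal roll-over and equal LTE exposure per entrant in both arms. A reader might take 1.5 as a ceiling, but for D5180C00007 it is the value at full roll-over, and lower roll-over raises it.

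The practical loss is limited to the SAF predecessor-period column and to any sign of period mix in the primary table. The change should be made, but it does not threaten the LTE-year safety comparison.

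**What to change.** 1. In SAP 4.5.1 and Table 10, restore the by-period AE columns for Randomised Tezepelumab and Randomised Placebo in the SAF, as Protocol 9.4.2 requires.
2. Add a supportive period-stratified exposure-adjusted rate that applies the same period weights to both arms. Neither document promises this, but the columns only expose the period mix, whereas this rate removes it.
3. If the columns are not restored, declare the change in SAP Section 6 and footnote the overall AE table to direct readers to the SAF-LTE LTE-period comparison.
4. Add the already logged change to the important-deviation summaries to Section 6.

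The cost is SAP wording and some extra columns. The periods are already defined in SAP 3.1.5.1, and no new data are needed.
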